6.1.2. Adjustments for Covariates

Where statistical modelling is performed, the baseline value of that assessment will be used as a covariate.

6.1.3. Multiple Comparisons

This section details the null hypotheses for this study, which are presented in the form H_{ij} , where i = treatment period ($i = 1$) and j = hypothesis number ($j = 1, 2, 3, 4$).

The hypothesis relating to the primary endpoint is:

H_{11} : SMPG-detected hypoglycemia episode rate _{dasiglucagon} = SMPG-detected hypoglycemia episode rate _{SOC only}

The hypotheses relating to the key secondary endpoints are:

H_{12} : Increase in fasting tolerance _{dasiglucagon} = increase in fasting tolerance _{SOC only}

H_{13} : CGM percent time in range _{dasiglucagon} = CGM percent time in range _{SOC only}

H_{14} : Clinically significant SMPG-detected hypoglycemia episode rate _{dasiglucagon} = clinically significant SMPG-detected hypoglycemia episode rate _{SOC only}

A fixed-sequence statistical strategy will test the primary (Section 2.2.1.1) and 3 key secondary endpoints of Treatment Period 1 (Section 2.2.1.2) in a pre-defined order, all at the same significance level ($\alpha = 0.05$ for the final analysis) to maintain an overall Type I error rate of at maximum $\alpha = 0.05$, moving to a second endpoint only after a success on the previous endpoint. Failure at any stage in the sequence implies automatic failure at all subsequent stages. All P values for each comparison without adjustments will be provided in the summary tables for informational purposes.

The test hierarchy is:

Treatment Period 1

- H₁₁: SMPG-detected hypoglycemia episode rate during Weeks 2-4 of the treatment period (primary endpoint)
- H₁₂: Increase in fasting tolerance (i.e., time from meal to PG <70 mg/dL) from baseline to Weeks 2-4 of the treatment period (key secondary endpoint)
- H₁₃: CGM percent time in range 70-180 mg/dL (3.9-10.0 mmol/L) during Weeks 2-4 of the treatment period (key secondary endpoint)
- H₁₄: Clinically significant SMPG-detected hypoglycemia episode rate, defined as average weekly number of episodes <54 mg/dL (3.0 mmol/L) during Weeks 2-4 of the treatment period (key secondary endpoint)

6.1.4. Handling of Dropouts or Missing Data

6.1.4.1. Premature Withdrawal from Study

Patients who withdraw from the study prematurely will not be replaced. If a substantial number of patients withdraw prematurely, the sponsor will evaluate the need for developing replacement criteria.

Randomized patients who subsequently withdraw from the trial may not re-enter. The patient number from a withdrawn patient will not be reassigned to another patient.

6.1.4.2. Imputation of Missing Event Data

For analysis of primary endpoint and key secondary endpoint of clinically significant hypoglycemia events, a jump-to-control (J2C) multiple imputation (MI) method, using SAS procedures PROC GENMOD, PROC GLMMOD, PROC SCORE, and PROC MIANALYZE, will be performed to handle missing data; note that missing count data following a negative binomial distribution cannot be analyzed in PROC MI, so additional steps must be taken to impute the missing data. Due to the expectation of rapid metabolism and excretion of trial drug, it is expected that efficacy would be similar to the control group in cases of premature treatment discontinuation; thus, the J2C method is appropriate to handle missing values in this situation (considered missing not at random [MNAR]). Since the primary endpoint is an event, it is possible that the event will not occur before discontinuation of study drug or end of Treatment Period 1; in that case, the number of events will be considered as 0.

The analysis will have 3 broad components: i) the MI process for the SOC-only data; ii) the MI process for the dasiglucagon + SOC patients' data; and iii) the analysis model that will be used to draw inference regarding the primary causal estimand, along with the method for combining the

results across the multiply-imputed datasets. These will be carried out in 6 steps, as outlined below. The seed to be used in the analysis is 12255070. The algorithm will use 20 burn-in iterations before each imputation, and 1000 imputed datasets will be created for the analysis for each of components i and ii. The methodology for imputing missing count data is based off of work by Keene et al.⁴

1. All observed data will be fitted using a Bayesian negative binomial model with a log link using PROC GENMOD using treatment and region as fixed effects (and class variables) and baseline event rate as a covariate. A thinning rate of 20, number of burn-ins of 20, number of iterations after burn-in of 20000, and a seed of 12255070 will be used in the analysis. Since the thinning parameter selects every 20th of the 20000 iterations, 1000 imputations are performed. The sampled posterior parameter estimates will be output; that dataset will be used in a later step, when PROC SCORE is utilized.
2. Design matrices will need to be created for each subject that displays their parameterization for the model. To create the design matrices, a dataset will need to be created that has records representing: (1) the observed total number of hypoglycemia events per patient in Treatment Period 1, from Day 1 through the end of Treatment Period 1 or trial discontinuation, whichever is earlier; (2) the data that will be used to model event rate before trial discontinuation; and (3) the data that will be used to model the event rate after trial discontinuation (this will be the same as the data in 1, however, the treatment will be set to the SOC-only arm). The design matrices will be created using PROC GLMMOD, using the same model as was used in PROC GENMOD previously.,
3. Generate the predicted number of events from the pre-discontinuation dataset without taking time-in-study into account. This will be done by using PROC SCORE to multiply design matrix corresponding with dataset (2) from Step 2 above with the parameter estimates from the Bayesian posterior model in Step 1. Note that the dataset described in Step 2 has been merged with study exposure time in Treatment Period 1, log of study exposure time in Treatment Period 1, treatment, region, baseline number of events, and observed post-baseline number of events. Similarly, generate the predicted number of events from the post-discontinuation dataset without taking time-in-study into account, by using PROC SCORE to multiply the design matrix corresponding with dataset (3) from Step 2 with the parameter estimate from the Bayesian posterior model in Step 1.
4. To complete the imputation, merge the two scored datasets together by sequential record number. For cases where predicted values from the pre-withdrawal and post-withdrawal datasets are known, derive the following parameters:
 - a. Inversion of dispersion parameter: $k = 1/dispersion$
 - b. Predicted number of events accounting for length of time in Treatment Period 1 before withdrawal:
$$\hat{y}_1 = e^{Predicted\ Y,pre-wd} \times time\ in\ Treatment\ Period\ 1$$
 - c. Predicted number of events accounting for length of time in Treatment Period 1 after withdrawal:
$$\hat{y}_2 = e^{Predicted\ Y,post-wd} \times \max(28 - time\ in\ Treatment\ Period\ 1, 0)$$

$$d. \text{ Conditional probability: } p_{cond} = \frac{k+\hat{y}_1}{k+\hat{y}_1+\hat{y}_2}$$

Then impute the counts as follows:

- i. If patient completed Treatment Period 1 or the event is impossible or unlikely (i.e., $p_{cond} > 0.999999$), then $\text{count}_{\text{impute}0} = \text{count}_{\text{observed}}$.
- ii. If patient discontinued before the end of Treatment Period 1 but k is large (i.e., dispersion is close to zero; $k > 1 \times 10^{20}$) then $\text{count}_{\text{impute}0} = \text{rand}(\text{'Poisson'}, \hat{y}_2)$.
- iii. If patient discontinued before the end of Treatment Period 1 and k is not large then $\text{count}_{\text{impute}0} = \text{rand}(\text{'NEGATIVEBINOMIAL'}, p_{cond}, k + \text{count}_{\text{observed}})$.

Note that the number of events before discontinuation must be added and the number of events in Week 1 must be subtracted, since the primary endpoint is number of events in Weeks 2-4.

If patient discontinued after Week 1 then the number of events in Week 1 is based on the observed data, using the study weeks as outlined in Section 6.1.7.

For case i. $\text{count}_{\text{impute}} = \text{count}_{\text{impute}0} - \# \text{ events in Week 1}$

For case ii. and iii. $\text{count}_{\text{impute}} = \text{count}_{\text{observed}} + \text{count}_{\text{impute}0} - \# \text{ events in Week 1}$

If patient discontinued during Week 1, then

$$\text{count}_{\text{impute}} = \text{ceil}[\text{count}_{\text{impute}0} \times (1 - \frac{7 - \text{time in Treatment Period 1}}{28 - \text{time in Treatment Period 1}})].$$

5. The analysis model will be a negative binomial regression with number of hypoglycemia episodes during Weeks 2-4 as the dependent variable, and all covariates from the primary analysis model. The causal estimand will be estimated using the difference in the least squares means between the 2 treatment groups in each of the 1000 imputed datasets.
6. The negative binomial regression results from the multiply-imputed datasets will be combined using the usual Rubin's rules for multiple imputation⁵ and will be done in SAS using PROC MIANALYZE. A significance test of the treatment difference will be tested at the 2 sided α level ($\alpha = 0.05$), and corresponding CIs (based on the respective α values) will be calculated.

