8.4. Treatment Discontinuation

To prevent missing data, patients should, to the extent possible, be kept in the trial; therefore, treatment discontinuation is often the preferred option in case of e.g., substantial noncompliance with trial procedures or initiation of prohibited treatment that interferes with the efficacy and safety evaluation. If it is an investigator's decision to discontinue the patient's treatment, the investigator should, whenever possible, discuss the potential discontinuation of the treatment with the medical monitor. If the patient is discontinued from trial treatment by the investigator, or withdraws consent for trial treatment the reason for treatment discontinuation and the date of treatment discontinuation will be recorded on the appropriate page of the eCRF. The patient should be asked to continue in the trial by following the planned visit schedule. At a minimum the patient will be asked to attend the Follow-up Visit 28 days (± 3 days) after discontinuation of trial treatment.

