3.1. Overall Design

3.2. Sample Size and Power

A total of up to 32 patients will be randomized if they have at least 3 events of hypoglycemia on average per week, as recorded in the diary during the 2 weeks prior to randomization. It is assumed that patients continuing on SOC will maintain a similar level through Treatment Period 1, with the number of hypoglycemia events (PG <70 mg/dL or 3.9 mmol/L) during Weeks 2-4, as detected by SMPG following a Poisson distribution with a mean of 9. The trial is powered to detect a treatment effect of 50%, hence, assuming that the number of hypoglycemia events reported for patients in the dasiglucagon group during Weeks 2-4 will follow a Poisson distribution with a mean of 4.5. At the final analysis, 32 patients will have 99% power testing at a 0.05 significance level. The overall alpha level is strongly controlled in this setting, remaining at or below 0.05.

This sample size was calculated before cancellation of interim analysis, this is why it refers to interim analysis. Cancellation of interim analysis (see Section 10), does not imply new sample size calculation.

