4.1. Introduction

Data processing, tabulation of descriptive statistics, calculation of inferential statistics, and graphical representations will be performed primarily using SAS (release 9.4 or higher). If the use of other software is warranted, the final statistical methodology report will detail what software was used for what purposes.

Continuous (quantitative) variable summaries will include the number of patients (n) with non-missing values, mean, standard deviation (SD), median, minimum, and maximum.

Categorical (qualitative) variable summaries will include the frequency and percentage of patients who are in the particular category or each possible value. In general, the denominator for the percentage calculation will be based upon the total number of patients in the study population for the within each treatment group, unless otherwise specified. The denominator for by-visit displays will be the number of patients in the relevant study population with non-missing data at each visit.

The minimum and maximum will be reported with the same degree of precision (ie, the same number of decimal places) as the observed data. Measures of location (mean and median) will be reported to 1 degree of precision more than the observed data and measures of spread (SD) will be reported to 2 degrees of precision more than the observed data.

Percentages will be presented to 1 decimal place, unless otherwise specified.

Unless otherwise indicated, all testing of statistical significance will be 2-sided with a significance level of $\alpha = 0.05$ (see Section [10 Changes from Planned Analysis](#)).

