6.1.4.3. Imputation of Missing Non-Event Data

For analysis of key secondary endpoints of fasting tolerance, and CGM percent time in range, a J2C MI method, with SAS procedures PROC MI and PROC MIANALYZE, will be performed to impute missing data for patients who have discontinued treatment. Any missing values occurring before the patient discontinues/completes treatment will be imputed during the monotone step based on the data from the same treatment group (considered missing at random [MAR]).

The analysis will have 3 broad components:

- i) the MI process for the non-monotone data;
- ii) the MI process for the monotone data
 - a. J2C MI method for missing data for patients who discontinue treatment

- b. Monotone regression [MAR] for missing values occurring before the patient discontinues/completes treatment
- iii) iii) the analysis model that will be used to draw inference regarding the primary causal estimand, along with the method for combining the results across the multiply-imputed datasets.

The seed to be used in the analysis is 12255070. The algorithm will use 20 burn-in iterations before each imputation, and 1000 imputed datasets will be created for the analysis for each of steps i and ii

- Step i) description:

Imputation of non-monotone data (missing data at intermediate visits) using PROC MI based on Markov Chain Monte Carlo (MCMC) methodology (considering MAR and using impute=monotone options to impute only the non-monotone data). Variables treatment, baseline region and weekly values will be included in this model. .

This first imputation step will produce 1000 datasets with a monotone missing pattern.

- Step ii)

- a- analysis for missing data for subjects who discontinue treatment:

Missing post-withdrawal monotone data will be imputed in a sequential manner, using a method proposed by Ratitch and O'Kelly, 2011⁷. Due to the expectation of rapid metabolism and excretion of trial drug, it is expected that efficacy would be similar to the control group in cases of premature treatment discontinuation; thus, the J2C method is appropriate to handle imputation of monotone data (missing data after premature treatment discontinuation, considered MNAR – control-based pattern imputation).

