If subject discontinues trial before reaching Week 9:			
Week 2	Days 8 – 14	Date 1 date + 7 days	Earliest of Analysis Start Date + 6 days, or date of trial discontinuation
Week 3	Day 15 – 21	Date 1 date + 14 days	Earliest of Analysis Start Date + 6 days, or date of trial discontinuation
Week 4	Days 22 – 28	Date 1 date + 21 days	Earliest of Analysis Start Date + 6 days, or date of trial discontinuation
Weeks 2-4	Days 8 – 28	Same as Week 2 Analysis Start Date	Same as latest of Week 2, Week 3, or Week 4 Analysis Stop Date
Week 5	Days 29 – 35	Week 5 date	Earliest of Analysis Start Date + 6 days, or date of trial discontinuation
Week 6	Days 36 – 42	Week 5 date + 7 days	Earliest of Analysis Start Date + 6 days, or date of trial discontinuation

Study Week	Planned Days	Analysis Start Date	Analysis Stop Date
Week 7	Days 43 – 49	Week 5 date + 14 days	Earliest of Analysis Start Date + 6 days, or date of trial discontinuation
Week 8	Days 50 – 56	Week 5 date + 21 days	Earliest of Analysis Start Date + 6 days, or date of trial discontinuation
Weeks 6-8	Days 36 – 56	Same as Week 6 Analysis Start Date	Same as latest of Week 6, Week 7, or Week 8 Analysis Stop Date

- **Study Visit** = in-clinic visit as per the schedule of events, to be used for assessments that can only occur during a clinic visits (e.g., PedsQL, safety assessments like clinical laboratory assessments and vital signs).
- **Change from baseline** = value at current time point – value at baseline.
- **TEAE** = an AE with an onset at the time of or following the start of treatment with the trial drug (dasiglucagon + SOC arm) or date/time of randomization (SOC only arm) through the Follow-up visit or Early Termination visit, whichever occurs first.
- **PK Clearance:**

$$CL/f \text{ (L/h)} = R_0/C_{ss}$$

where R_0 = infusion rate (pmol/h) and C_{ss} = concentration at steady state (pmol/L), weight ($1\mu\text{g/kg/hr} = 295.7 \text{ nmol/kg/h}$)

- **SMPG-detected Hypoglycemia episode** = PG <70 mg/dL or 3.9 mmol/L, as detected by SMPG and reported in the eCRF. A single hypoglycemia episode is defined as up until 60 minutes from the start of the episode even if normoglycemia (>70 mg/dL) is not reached within this time. A new episode of hypoglycemia is to be reported when the next PG value below 70 mg/dL (3.9 mmol/L) is measured. Episodes are defined as the ones entered in the eCRF, no statistical programming will be done to define an episode.

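### The count imputation for H11 and H14 runs to trial discontinuation although its rationale is treatment discontinuation, so on a literal reading a child who stops dasiglucagon and sends no more data is scored event-free

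*SAP*

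**What the plan says.** SAP 6.1.4.2 governs the primary endpoint (H11) and the <54 mg/dL endpoint (H14). Its reason for J2C is that "it is expected that efficacy would be similar to the control group in cases of premature treatment discontinuation".

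The algorithm uses another date. In Step 2 the observed count runs "from Day 1 through the end of Treatment Period 1 or trial discontinuation, whichever is earlier", and the record that moves a child to the SOC rate covers the time after trial discontinuation. Step 4 imputes over max(28 − time in Treatment Period 1, 0) days. The early-termination rows of SAP 6.1.7 end each study week at "Earliest of Analysis Start Date + 6 days, or date of trial discontinuation".

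For fasting tolerance and time in range, SAP 6.1.4.3 applies J2C on the other trigger: it "will be performed to impute missing data for patients who have discontinued treatment". SAP 10 records that the imputation was split into event and non-event methods, but mentions no change of trigger. SAP 7.1 tabulates withdrawal from treatment and withdrawal from the trial separately, so the SAP itself treats them as different events.

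Protocol 8.4 makes the two dates diverge. A child who stops treatment is asked to keep to the visit schedule, and failing that: "At a minimum the patient will be asked to attend the Follow-up Visit 28 days (± 3 days) after discontinuation of trial treatment". The Schedule of Events shows no diary review at the Follow-up Visit. Under SAP 6.1.7 only episodes entered in the eCRF count.

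**The concern.** J2C is there for the child who stops the drug and whose later outcome is unknown. If the clock follows trial participation, that child can pass through Weeks 2-4 with no data and still count as fully observed. Because an episode exists only if it was entered, silence becomes a count of zero over three full weeks. That contradicts the plan's own assumption that such a child returns to the control rate.

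The planned checks would not reveal it. The no-imputation sensitivity analysis in SAP 8.1.2 takes its offset from the same Weeks 2-4 period. If such children were the only gaps, the trial clock would show nothing missing; then SAP 8.1.1 skips multiple imputation and SAP 8.1.2 does not run the sensitivity analysis. For H14, SAP 8.2.1 states no offset for the main model, so the count would enter unadjusted.

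**Working it through.** **Inputs.** SOC count in Weeks 2-4 "following a Poisson distribution with a mean of 9", dasiglucagon mean 4.5, 32 patients (SAP 3.2); 1:1 allocation, so 16 per arm (SAP 3.5). SAP 4.1 states that "all testing of statistical significance will be 2-sided with a significance level of" 0.05. Daily rates over 21 days: SOC 9/21 = 0.4286, dasiglucagon 4.5/21 = 0.2143. The number of stoppers, the stop day and any overdispersion are assumptions; the German protocol (20.4.3) anticipated no formal drop-out rate.

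**Plan's own figure.** SAP 3.2 says "32 patients will have 99% power testing at a 0.05 significance level". With a Wald test on the log rate ratio, SE = √(1/(16×9) + 1/(16×4.5)) = 0.1443; ln 2/0.1443 − 1.96 = 2.84, a power of 99.8%. The stated figure is reproduced to within a percentage point.

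**When the Follow-up Visit falls.** A stop on Day d puts it on Day d+25 to d+31. For d = 4 the earliest day is 29, so for every stop from Day 4 on the child is still in the trial when Treatment Period 1 ends. For a stop on Days 1-3 with the visit at the early edge of its window (Day 26-28), at most 2 days remain to impute.

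**What Step 4 then does.** Time in Treatment Period 1 = 28, so ŷ₂ = rate × max(28 − 28, 0) = 0 and p_cond = (k + ŷ₁)/(k + ŷ₁ + 0) = 1. This exceeds 0.999999, so rule i returns the observed count; rule iii would also draw zero at p = 1. With no Week 5 visit the main study-week table has no anchor date. The early-termination table, with trial exit after Day 28, gives the full 21 days, so the offset is log(3).

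**Expected Weeks 2-4 count for one child whose data end on the stop day.**

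| Stop day | Observed | J2C for the remaining days | As written | Under J2C |
|---|---|---|---|---|
| 7 | 0 | 21 × 0.4286 = 9.0 | 0 | 9.0 |
| 14 | 7 × 0.2143 = 1.5 | 14 × 0.4286 = 6.0 | 1.5 | 7.5 |
| 21 | 14 × 0.2143 = 3.0 | 7 × 0.4286 = 3.0 | 3.0 | 6.0 |

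**Expected rate ratio with m stoppers among 16 on dasiglucagon.** [(16 − m) × 4.5 + m × child's count]/(16 × 9):

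- One Day 7 stopper: 67.5/144 = 0.469 as written; 76.5/144 = 0.531 under J2C.
- Two Day 7 stoppers: 63/144 = 0.438 as written; 81/144 = 0.563 under J2C.
- One Day 14 stopper: 69/144 = 0.479 as written; 75/144 = 0.521 under J2C.

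**If the drug had no effect** (both means 9), Day 7 stoppers would give ratios of 15/16 = 0.94 with one and 14/16 = 0.875 with two. In simulation (negative binomial Wald test, treatment term only, 4000 runs per setting), false rejection in favour of dasiglucagon, nominally 2.5%, with zero, one and two such children was 2.3%, 6.2% and 9.8% with no overdispersion, and 3.7%, 5.0% and 6.5% with an assumed dispersion of 0.5.

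**The opposite direction.** One SOC child who stays enrolled but supplies nothing after Day 7 would also score 0. The ratio becomes (16 × 4.5)/(15 × 9) = 72/135 = 0.533, against a planned 0.5.

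**The case against.** The strongest reply is that the zero score is not written anywhere. The SAP does not define time in Treatment Period 1, and 6.1.4.2 mixes treatment discontinuation, trial discontinuation, withdrawal and study exposure time. The protocol lists Treatment Period 1 and the Follow-up Period separately, so a child seen only at Follow-up has arguably left Treatment Period 1 without completing it. Rules ii and iii refer to discontinuing before the end of that period without saying from what, and the partial-week rule in 6.1.7 has no qualifier either. A programmer could clock to the drug stop and impute as intended. This stands: a reader might infer that the SAP demonstrably scores these weeks as zero, but the documents support that only as the literal reading of Step 2 and the 6.1.7 rows.

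The affected child also departs from planned conduct. Protocol 8.4 first asks for the normal visit schedule, the diary runs to Visit 7, and meter data are downloaded at each visit. For a stopper who keeps supplying data, the trial clock is correct under the treatment-policy estimand. This also stands, and narrows the problem to children in the trial without data.

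Finally, an analysis excluding data after drug discontinuation is mentioned. It is optional and ad hoc, so it does not protect the primary result.

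**Conclusion.** The point holds as a conflict between the rationale of SAP 6.1.4.2 and its own Steps 2-4, and between that section and 6.1.4.3. The date that decides whether J2C applies in the primary analysis should not be left to interpretation. The size depends on how many children stop dasiglucagon in Treatment Period 1 and then supply no glucose data; the documents do not give that number, and with none the bias is zero. The Day 7 figures are near the worst case: the gap per child falls from 9.0 events (Day 7) to 6.0 (Day 14) and 3.0 (Day 21).

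Two stronger conclusions are tempting and not supported. The first is that the error can only favour dasiglucagon. That is its direction for drug stoppers, since only that arm can stop trial drug in Treatment Period 1, but 6.1.4.2 has no rule for within-trial gaps in either arm, and silent SOC children push the ratio the other way. The second is that children lost to follow-up are caught as well because of the contact attempts in protocol 8.3. That section does not say which date is recorded as discontinuation, so nothing shows that it trails the last data.

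**What to change.** In SAP 6.1.4.2 Steps 2-4 and the early-termination rows of 6.1.7, for both arms:

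- End observed time at the last day in Treatment Period 1 with evaluable SMPG monitoring, shown by meter download or a completed diary. The last recorded episode must not be used, because a child can be monitored and event-free.
- Keep all data recorded after the drug is stopped, in line with treatment policy.
- Impute the remaining days to Day 28 from the SOC rate for children off dasiglucagon and for children in the SOC arm.
- Impute gaps while a child is still on dasiglucagon from the same arm under missing at random. Protocol 12.4.3.4 already states this, but the SAP keeps it only for non-event data.
- Use the same observed time for the offset in the no-imputation sensitivity analysis.

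The cost is SAP wording and one date derivation from meter and diary data already collected. The estimate may be slightly less favourable to dasiglucagon.

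### SAP 6.1.4.2, Step 4: when the sampled dispersion is below about 1e-7 to 3e-7, the p_cond test drops all future events for children who leave after Week 1 and blocks the Poisson draw meant for that case

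*SAP*

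**What the plan says.** SAP 6.1.4.2 covers missing counts for the primary endpoint and for the <54 mg/dL key secondary endpoint. Step 4 takes k as the inverse of the sampled dispersion. It takes y1 as the predicted events up to leaving, and y2 as the predicted events for the rest of the 28 days at the SOC-only rate. It then sets p_cond = (k + y1)/(k + y1 + y2) and lists three rules:

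- Rule i, "If patient completed Treatment Period 1 or the event is impossible or unlikely", the second part meaning p_cond above 0.999999: keep the observed count.
- Rule ii, "If patient discontinued before the end of Treatment Period 1 but k is large" (k above 10^20): draw the future count from a Poisson distribution with mean y2.
- Rule iii, "If patient discontinued before the end of Treatment Period 1 and k is not large then": draw it from a negative binomial with parameters p_cond and k plus the observed count.

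No order of evaluation is given beyond the listing. Under rules ii and iii the observed count is added back and Week 1 events are subtracted. Under rule i Week 1 events are only subtracted. A separate formula applies "If patient discontinued during Week 1, then": the count from rules i-iii is multiplied by 21/(28 - t), with t the days in the period, and rounded up.

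SAP 8.1.1 gives patients with imputed data an offset of log(3), and runs no multiple imputation if nothing is missing. Step 1 gives the chain settings but no prior for the dispersion. SAP 3.2 plans on SOC counts "following a Poisson distribution with a mean of 9" over Weeks 2-4.

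**The concern.** Rule i uses p_cond as if it measured whether further events are likely. It does not: p_cond approaches 1 either because y2 is near zero or because k is very large. In the second case the future count is simply Poisson with mean y2, which is what rule ii is meant to supply. As listed, rule i catches those draws first and supplies nothing.

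At stake is the jump-to-control assumption behind the primary analysis. A dasiglucagon child who leaves should accrue events at the SOC rate afterwards. In an affected draw that child accrues none, yet is analysed with three full weeks of exposure. With 16 children per arm, one leaver is enough to move the estimate.

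**Working it through.** **1. The plan's own figures.** With means 9 and 4.5 and 16 per arm, the standard error of the log rate ratio is sqrt(1/144 + 1/72) = 0.144. Then ln 2/0.144 = 4.80, and power is Phi(4.80 - 1.96) = 99.8%, in line with the stated 99%. The 20,000 iterations thinned by 20 give the stated 1000 imputations. Neither figure is in dispute.

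**2. When rule i applies to a leaver.** Solving (k + y1)/(k + y1 + y2) > 0.999999 gives k > 999,999 y2 - y1, so roughly k > 10^6 y2. Planning rates are 3 events per week on SOC (9/3) and 1.5 on dasiglucagon (4.5/3). For a leaver on day t, y2 = 3(28 - t)/7.

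| Leaves on day | y2 | rule i once k exceeds | dispersion below |
|---|---|---|---|
| 7 | 9.00 | 9.0e6 | 1.1e-7 |
| 10 | 7.71 | 7.7e6 | 1.3e-7 |
| 14 | 6.00 | 6.0e6 | 1.7e-7 |
| 21 | 3.00 | 3.0e6 | 3.3e-7 |

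**3. What the future count should be.** Rule iii has mean (k + observed)(1 - p_cond)/p_cond = (k + observed) y2/(k + y1), which tends to y2 as k grows. For a Day 10 dasiglucagon leaver (y1 = 2.14) whose observed count equals y1:
- k = 2, 10, 1000, 10^5 and 10^6 all go to rule iii with mean 7.71.
- k = 10^7 gives p_cond = 0.999999229, so rule i applies and the future count is 0.

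The imputation is therefore right up to the cutoff and falls to zero beyond it.

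**4. Rule ii.** At k = 10^20, p_cond equals 1 in double precision. Escaping rule i there would need y2 above about 10^14 events, so in listed order rule ii cannot be reached. Testing rule ii before rule i rescues only k above 10^20. Draws with k from about 10^7 to 10^20 stay wrong whichever of those two comes first, unless rule iii is also placed ahead of rule i, which would leave the p_cond clause idle for leavers.

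**5. Worst-case effect on the rate ratio.** Assume every draw is affected and dasiglucagon children leave on Day 10. Observed Weeks 2-4 events are 3 x 1.5/7 = 0.64. The count is 0.64 under rule i and 0.64 + 7.71 = 8.36 as intended. The SOC total is 16 x 9 = 144.

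| Leavers | Rule i | Intended |
|---|---|---|
| 1 | (15 x 4.5 + 0.64)/144 = 0.47 | (15 x 4.5 + 8.36)/144 = 0.53 |
| 2 | (14 x 4.5 + 1.29)/144 = 0.45 | (14 x 4.5 + 16.71)/144 = 0.55 |
| 3 | (13 x 4.5 + 1.93)/144 = 0.42 | (13 x 4.5 + 25.07)/144 = 0.58 |

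**6. Share of draws affected.** The SAP gives no dispersion prior, so the priors here are assumptions, in a two-arm model without covariates. Flat or Gamma(1, 1): about 0%. Gamma(0.001, 0.001) or Gamma(0.01, 0.01) with truly Poisson counts: 67-83% over simulated datasets, 88-99% in a separate grid integration. With these gamma priors the simulated share is 0-43% at a true dispersion of 0.25 and about 0% at 0.5. The two diffuse-prior results differ, so I rely only on the statement that most draws are affected in that setting.

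**7. Week 1 leavers.** Under rule i the observed Week 1 count is itself rescaled. With t = 3 and one observed event the result is ceil(21/25) = 1, against an intended mean of 9. Under rules ii and iii the draw is rescaled and rounded up. With Poisson counts at 3 per week the mean becomes 9.42 to 9.57 instead of 9.0 for t = 1 to 6. For one to three dasiglucagon leavers with t = 1 (excess 0.44), the rate ratio rises by 0.44/144 = 0.003 to 3 x 0.44/144 = 0.009. At the largest excess (0.57, t = 5) the same arithmetic gives 0.004 to 0.012.

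**The case against.** The best defence is that this is a guard condition that will rarely matter. Poisson is only the sample-size assumption, and the analysis model is negative binomial. Children aged 3 months to 12 years, with or without pancreatectomy and with no upper limit on baseline events, are unlikely to show residual dispersion below 1e-7. Children who stop treatment are asked to stay on the visit schedule (Protocol 8.4), and the imputation splits data at trial discontinuation. Period 1 lasts four weeks, and the German protocol (20.4.3) anticipates no formal drop-out rate. SAP 8.1.2 also requires the analysis without imputation, so a distortion could be seen beside it.

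All of this stands as a limit on how often the rule bites. It does not make the rule right: a diffuse prior can put posterior mass at tiny dispersions, and the SAP leaves the prior open. The unimputed analysis rests on a different assumption and lies outside the testing hierarchy.

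Some stronger readings are tempting and not supported:

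- A reader might infer that any near-Poisson draw is affected. Dispersions of 1e-3 or 1e-5 go to rule iii and are imputed correctly.
- A reader might infer that every early leaver gets zero. Week 1 leavers get a rescaled observed count, and later leavers keep the Weeks 2-4 events already observed.
- A reader might infer a built-in bias towards dasiglucagon. The direction follows the arm with leavers, and SOC leavers would move the ratio the other way.
- A reader might infer that every Week 1 count is rounded up. A zero or an exact integer product is unchanged (about 12% of Poisson draws at t = 1 or 4).

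**Conclusion.** The rule is wrong as written, within a narrow and conditional range. Rule i pre-empts the Poisson branch, and in draws with dispersion below about 1e-7 to 3e-7 it removes the jump-to-control events of children who leave after Week 1 while log(3) stays as their offset. I read SAP 8.1.1 as giving that offset to rule i leavers too, since it names no exception.

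The range of 0.47-0.42 against 0.53-0.58 is a ceiling: every draw affected, one to three dasiglucagon leavers on Day 10, planning rates. The realistic size lies between nothing and that ceiling, and the documents do not fix it because the prior is missing. Without Period 1 leavers there is no effect. The documents therefore do not support saying that the imputed primary counts are wrong in general. The rounding rule is minor: about 0.4 to 0.6 events per Week 1 leaver on a mean of 9, moving the ratio against dasiglucagon when the leavers are dasiglucagon children.

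**What to change.** In SAP 6.1.4.2, Step 4:

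1. Limit rule i to patients who completed Period 1 or whose y2 is itself negligible (for example y2 < 1e-6). Remove p_cond from that test.
2. Use the Poisson draw with mean y2 for any leaver whose k is so large that p_cond exceeds 0.999999, in place of the 10^20 cutoff.
3. For Week 1 leavers, set y2 to the daily SOC rate times 21 days and draw the Days 8-28 count directly, with no rescaling and no rounding up.
4. In Step 1, state the prior for the dispersion parameter.

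The cost is a few lines of SAP text and the matching code, before database lock. No data collection, patients or sample size are affected. The <54 mg/dL key secondary endpoint, which uses the same steps, is corrected at the same time.
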